Physical Measurements (including Performance Status)	X	Collect weight and ECOG Performance Status (Appendix 1) within 72 hours prior to dosing. Targeted physical examination may be performed if clinically indicated and is recommended to include cardiovascular, gastrointestinal, pulmonary and neurological exam for participants with brain metastases.
Vital Signs	X	Within 72 hours prior to dosing, tests includes temperature, BP, HR and RR
Serious Adverse Event Assessment	X	Assessed using NCI CTCAE v 4.0 (continuously monitored throughout treatment period)
Adverse Events Assessment	X	Assessed using NCI CTCAE v 4.0(continuously monitored throughout treatment period)
Review Concomitant Medication	X	
Laboratory Tests	X ^{a, b, c, d}	CBCs with differential ^a Serum chemistry tests ^b and liver function tests ^c should be checked every cycle, and the results should be obtained prior to dosing. Thyroid Function Test (TFTs) ^d should be checked every 6 weeks.
Pregnancy Test	Every 4 weeks	Completed more frequently if required by local standards (serum or urine as required by standard of care at the site).
Clinical Drug Supplies		
Administration of nivolumab (3 mg/kg)	X	All enrolled participants continue treatment every 2 Weeks. Treatment should be continued as long as clinical benefit is observed for a maximum of 24 weeks or until treatment is no longer tolerated by the participant or withdrawal of consent. Record Study Drug Infusion start and stop

BP = blood pressure; CBC = complete blood count; ECOG = Eastern Cooperative Oncology Group; HR = heart rate; LDH = lactate dehydrogenase; NCI CTCAE = National Cancer Institute Common Terminology Criteria for AEs; RR = respiratory rate.

[figure not shown]
^a CBCs with differential includes white blood cell count, lymphocyte count, absolute neutrophil count, hemoglobin, hematocrit, and platelet count. Results to be obtained prior to dosing on infusion days.

^b Serum chemistry tests include blood urea nitrogen (BUN) or serum urea level, serum creatinine, sodium, potassium, calcium, magnesium, phosphate, chloride, and glucose.

^c Liver function tests include AST, ALT, total bilirubin, alkaline phosphatase, albumin, LDH.

^d Thyroid function testing including TSH (reflex to free T3 and free T4 if abnormal result).

Table 2-3: CA209887: Follow-up Procedures

Procedure	Follow-up phase	Notes

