6.2 Exclusion Criteria

1) Medical Conditions

- a) Women who are pregnant or breastfeeding
- b) Women with a positive pregnancy test at enrollment or prior to administration of study medication
- c) Participants with untreated, symptomatic central nervous system (CNS) metastases.
- d) Participants with carcinomatous meningitis.
- e) Participants with active, known or suspected autoimmune disease. Participants with type I diabetes mellitus, hypothyroidism only requiring hormone replacement, skin disorders (such as vitiligo, psoriasis or alopecia) not requiring systemic treatment, or conditions not expected to recur in the absence of an external trigger are permitted to enroll

- f) Participants with a condition requiring systemic treatment with either corticosteroids (> 10 mg daily prednisone equivalent) or other immunosuppressive medications within 14 days of first dose of study drug. Inhaled or topical steroids, and adrenal replacement steroid doses > 10 mg daily prednisone equivalent, are permitted in the absence of active autoimmune disease.
- g) Other active malignancy requiring concurrent intervention.
- h) Participants with previous malignancies (except non-melanoma skin cancers, and the following in situ cancers: bladder, gastric, colon, endometrial, cervical/dysplasia, melanoma, or breast) are excluded unless a complete remission was achieved at least 2 years prior to study entry AND no additional therapy are ongoing and required during the study period with the exception of anti-estrogen/androgen therapy or bisphosphonates. Participants with other active malignancy requiring concurrent intervention are excluded.
- i) All toxicities attributed to prior anti-cancer therapy other than alopecia, fatigue, or peripheral neuropathy must have resolved to Grade 1 (NCI CTCAE version 4) or baseline before administration of study drug.
- j) Participants must have recovered from the effects of major surgery or significant traumatic injury at least 14 days before the first dose of study treatment.
- k) Known history of positive test for human immunodeficiency virus (HIV) or known acquired immunodeficiency syndrome (AIDS). NOTE: Testing for HIV must be performed at sites where mandated locally.

2) Prior/Concomitant Therapy

- a) Ongoing or planned administration of anti-cancer therapies other than those specified in this study

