4.2 Secondary Endpoints

- Incidence and severity of all treatment-related select AEs which are as follows
 - Pulmonary toxicity
 - Gastrointestinal toxicity (diarrhea or colitis)
 - Endocrinopathies
 - Hepatotoxicity (including asymptomatic liver function tests (LFT) elevations)
 - Renal toxicity
 - Skin toxicity
 - Neurological toxicity
 - Hypersensitivity/infusion reactions
- Incidence of all treatment-related SAEs
- Incidence of AEs that lead to discontinuation from treatment with nivolumab

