7.6.5 Select Adverse Events

Unless otherwise specified, analyses will be performed by select AE category. Some analyses may also be repeated by subcategory of endocrine events.

Select AEs includes:

- Pulmonary toxicity
- Gastrointestinal toxicity (diarrhea or colitis)
- Endocrinopathies
- Hepatotoxicity (including asymptomatic LFT elevations)
- Renal toxicity
- Skin toxicity
- Neurological toxicity
- Hypersensitivity/infusion reactions

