	Follow-up Visit 1: 30 days (+/- 5 days) after last dose or on the date of discontinuation (+/- 5 days) if date of discontinuation is greater than 35 days after last dose. Follow up Visit 2: 70 days (+/- 5 days) after Follow up Visit 1.	Participants who discontinue on-study treatment with nivolumab before 24 weeks will be followed for 100 days after the last on-study dose of nivolumab or for a maximum of 26 weeks from the date of the first on-study dose of nivolumab, whichever occurs earliest.
Safety Assessments		
Physical measurements	X	Collect weight and ECOG Performance Status. Focused physical examination may be performed if clinically indication.
Vital Signs	X	Temperature, BP, HR and RR.
Adverse Events Assessment	X	
Serious Adverse Event Assessment	X	All SAEs after 26 weeks of study duration for participants on commercial nivolumab supply will be reported to India Health Authority as part of spontaneous reporting.
Review Concomitant Medication	X	
Laboratory Tests	X	Laboratory tests as listed for on treatment assessment in Table 2-2.
Pregnancy Test	X	Completed more frequently if required by local regulations (serum or blood as required by standard of care at the site).

BP = blood pressure; ECOG = Eastern Cooperative Oncology Group; HR = heart rate; RR = respiratory rate.

Table 7.6-1: Select Adverse Events

Category	Subcategory	Preferred Terms
Endocrine Adverse Events	ADRENAL DISORDER	ADRENAL INSUFFICIENCY
		ADRENAL SUPPRESSION
		BLOOD CORTICOTROPHIN DECREASED
		BLOOD CORTICOTROPHIN INCREASED
	DIABETES	DIABETES MELLITUS
		LATENT AUTOIMMUNE DIABETES IN ADULTS
	PITUITARY DISORDER	HYPOPHYSITIS
	THYROID DISORDER	AUTOIMMUNE THYROIDITIS
		BLOOD THYROID STIMULATING HORMONE DECREASED
		BLOOD THYROID STIMULATING HORMONE INCREASED
		HYPERTHYROIDISM
		HYPOTHYROIDISM
		SECONDARY ADRENOCORTICAL INSUFFICIENCY
THYROID FUNCTION TEST ABNORMAL THYROIDITIS		
THYROXINE DECREASED		
THYROXINE FREE DECREASED		

Category	Subcategory	Preferred Terms
		THYROXINE FREE INCREASED THYROXINE INCREASED TRI-IODOTHYRONINE INCREASED
Hypersensitivity/Infusion Reactions		ANAPHYLACTIC REACTION HYPERSENSITIVITY INFUSION RELATED REACTION
Gastrointestinal Adverse Events		COLITIS DIARRHOEA ENTERITIS ENTEROCOLITIS FREQUENT BOWEL MOVEMENTS GASTROINTESTINAL PERFORATION

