Hepatic Adverse Events		ACUTE HEPATIC FAILURE ALANINE AMINOTRANSFERASE INCREASED ASPARTATE AMINOTRANSFERASE INCREASED BILIRUBIN CONJUGATED INCREASED BLOOD BILIRUBIN INCREASED HEPATIC ENZYME INCREASED HEPATIC FAILURE HEPATITIS HYPERBILIRUBINAEMIA LIVER DISORDER LIVER FUNCTION TEST ABNORMAL

Category	Subcategory	Preferred Terms
		TRANSAMINASES INCREASED
Pulmonary Adverse Events		ACUTE RESPIRATORY DISTRESS SYNDROME ACUTE RESPIRATORY FAILURE INTERSTITIAL LUNG DISEASE LUNG INFILTRATION PNEUMONITIS
Renal Adverse Events		BLOOD CREATININE INCREASED CREATININE RENAL CLEARANCE DECREASED HYPERCREATININAEMIA NEPHRITIS NEPHRITIS ALLERGIC RENAL FAILURE RENAL FAILURE ACUTE RENAL TUBULAR NECROSIS TUBULOINTERSTITIAL NEPHRITIS
Skin Adverse Events		BLISTER DERMATITIS DERMATITIS EXFOLIATIVE DRUG ERUPTION ECZEMA ERYTHEMA EXFOLIATIVE RASH PALMAR-PLANTAR ERYTHRODYSAESTHESIA SYNDROME

Category	Subcategory	Preferred Terms
		PHOTOSENSITIVITY REACTION
		PRURITUS
		PRURITUS ALLERGIC
		PRURITUS GENERALISED
		PSORIASIS
		RASH
		RASH ERYTHEMATOUS
		RASH GENERALISED
		RASH MACULAR
		RASH MACULO-PAPULAR
		RASH PAPULAR
		RASH PRURITIC
		SKIN EXFOLIATION
		SKIN IRRITATION
		URTICARIA
Neurological toxicity		NEUROTOXICITY

Source: MedDRA version 16

[REDACTED]

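### SAP Table 7.6-1 has no specific preferred term for an alkaline phosphatase increase or for type 1 diabetes, so related events coded to those terms fall outside the select-AE secondary endpoint

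*SAP*

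**What the plan says.** **Endpoint.** Treatment-related select AEs are the first-listed secondary endpoint. SAP 4.2 names the hepatic category as "Hepatotoxicity (including asymptomatic liver function tests (LFT) elevations". SAP 7.6.5 and Protocol 10.3.2.2 define it the same way.

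**What counts as a liver test.** Protocol Table 2-2, footnote c, states: "Liver function tests include AST, ALT, total bilirubin, alkaline phosphatase, albumin, LDH". The SAP's schedule of activities repeats this. The panel is drawn every cycle.

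**How events are assigned.** SAP 7.6.5.1 refers to Table 7.6-1 to identify select AEs and summarises them by category or subcategory, preferred term and worst grade.

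**The hepatic list.** It opens with acute hepatic failure and the ALT and AST increases, continues with "BILIRUBIN CONJUGATED INCREASED BLOOD BILIRUBIN INCREASED HEPATIC ENZYME INCREASED HEPATIC FAILURE HEPATITIS HYPERBILIRUBINAEMIA LIVER DISORDER LIVER FUNCTION TEST ABNORMAL", and ends with transaminases increased.

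**The endocrine list.** The diabetes subcategory holds diabetes mellitus and "LATENT AUTOIMMUNE DIABETES IN ADULTS". The thyroid terms end with "THYROXINE FREE INCREASED THYROXINE INCREASED TRI-IODOTHYRONINE INCREASED", and that last term is the only one for T3.

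**Upkeep.** The table is sourced to MedDRA version 16. SAP 7.6.7 gives a quarterly term review for the immune-mediated AE list. No such rule is stated for the select-AE list.

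**The concern.** The endpoint is described in words in one place and put into operation by a fixed term list in another, and the two do not fully match. Alkaline phosphatase is a liver test by the plan's own definition, and an isolated rise in it is a liver-test elevation. If the event is coded to a term naming that enzyme, the list does not pick it up. Likewise, a related event coded specifically as type 1 diabetes has no row in the diabetes subcategory.

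Whether such an event counts would then turn on how the investigator words the report and how it is coded, not on what happened to the participant. The error runs one way: a missing term can remove a participant from a category but never add one. This is a safety study done as a post-marketing commitment (Protocol 9.1), and category incidence of select AEs is one of its main outputs.

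**Working it through.** The plan gives no figure for this point, so the main check is a term-by-term reading.

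**1. Hepatic list.** There are 12 terms: acute hepatic failure; ALT increased; AST increased; conjugated bilirubin increased; blood bilirubin increased; hepatic enzyme increased; hepatic failure; hepatitis; hyperbilirubinaemia; liver disorder; liver function test abnormal; transaminases increased.

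| Protocol liver test | Specific term listed? |
|---|---|
| ALT | yes |
| AST | yes |
| Total bilirubin | yes |
| Alkaline phosphatase | no |
| LDH | no |
| Albumin | no |

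Three general terms could also catch an alkaline phosphatase event: hepatic enzyme increased, liver disorder, and liver function test abnormal.

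**2. Loss of text in conversion?** Unlikely. The 12 terms are in alphabetical order and run on without a break where an alkaline phosphatase term would sort.

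**3. Endocrine list.** There are 20 terms. Two are diabetes terms, neither specific to type 1. One is a T3 term (increase only, not free T3). T4 has total and free terms in both directions.

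**4. Effect of one missed participant,** 100 × 1/n, at the planned numbers:
- pooled: 100/100 = 1.0 point
- NSCLC: 100/70 = 1.4 points
- RCC: 100/30 = 3.3 points

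A participant is missed only if no other listed term in the same category applies to them.

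**5. Illustration only.** The documents give no rate for isolated alkaline phosphatase events. Assume 5 of 100 participants have a listed hepatic select AE and 0 to 5 more have only an unlisted one. Intervals are exact Clopper-Pearson, as in SAP Table 5-1.

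| Additional participants | Incidence | 95% CI (%) |
|---|---|---|
| 0 | 5% | 1.64 to 11.28 |
| 1 | 6% | 2.23 to 12.60 |
| 3 | 8% | 3.52 to 15.16 |
| 5 | 10% | 4.90 to 17.62 |

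The first and last rows reproduce the 5% and 10% entries at n = 100 in Table 5-1, which confirms the method.

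**The case against.** **General terms are listed.** This stands in part. An alkaline phosphatase rise coded as liver function test abnormal or hepatic enzyme increased counts, and type 1 diabetes coded as diabetes mellitus counts. Protocol 9.2.6 also prefers clinical to laboratory terms. A reader might infer that these events cannot count at all; the documents do not support that. But the preference applies only where possible, and a symptom-free rise in one enzyme may have no clinical term. The list also names ALT and AST individually beside the general terms, so it does not rely on the general terms for other enzymes.

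**Being in the panel does not make a test a hepatotoxicity marker.** LDH and albumin are in the same panel and have no term either. The liver eligibility limits in Protocol 6.2 use only AST/ALT and bilirubin. So leaving alkaline phosphatase out may be a choice of scope. That is possible, but the plan does not say so. Low albumin is not an elevation. Unlike LDH, alkaline phosphatase is used by the protocol as a liver marker: the drug-induced liver injury definition in Protocol 9.2.7 treats a raised value as a sign of cholestasis.

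**The T3 gap has little weight.** This stands. On study, free T3 is run only after an abnormal TSH, and TSH increases and decreases are both listed. A case is missed only if T3 alone is reported.

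**The protocol's mention of type 1 diabetes is an eligibility exception.** This also stands. Protocol 6.2 says "Participants with type I diabetes mellitus, hypothyroidism only requiring hormone replacement" may enrol. A reader might infer that this wording defines the endpoint; it does not. The point rests only on the absence of a specific term in the list. Diabetes mellitus is also analysed as an immune-mediated endocrine event under SAP 7.6.7.

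**The events are reported elsewhere.** True. Related AEs appear by preferred term under SAP 7.6.4, and Protocol 10.3.2.2 summarises liver and thyroid laboratory abnormalities by worst grade. That limits the harm but does not bring the category into line with its definition.

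**Conclusion.** The point holds as a gap in the operational definition of a secondary endpoint. Followed as written, a treatment-related event coded specifically to an alkaline phosphatase increase or to type 1 diabetes drops out of its select-AE category unless a listed general term is used. Hepatic and endocrine select-AE incidence can therefore be understated but not overstated by this route. The alkaline phosphatase omission is the stronger part, because the endpoint wording and the plan's own definition of liver tests both bear on it. The T3 terms are a matter of completeness.

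The size cannot be estimated from the documents. What can be stated is the unit cost per missed participant: 1.0 point pooled, 1.4 in NSCLC, 3.3 in RCC. A reader might infer a sizeable bias in the smaller group, since two missed RCC participants would be 2/30 = 6.7 points. Nothing in the documents supports that count or any other. Protocol 9.2.6 also restricts which laboratory abnormalities are recorded as AEs: those that are clinically significant or serious, that interrupt or stop treatment, or that need corrective therapy. The primary endpoint, sample size and laboratory summaries do not change.

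The conclusion assumes that Table 7.6-1 is applied as printed and that coding goes to the specific term when the report is specific.

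**What to change.** Before database lock, do one of the following.

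- **Add terms to Table 7.6-1**, using the preferred-term names in the dictionary version used for coding: alkaline phosphatase increased (hepatic) and type 1 diabetes mellitus (endocrine, diabetes). For completeness only, add T3 decreased and free T3 increased and decreased (endocrine, thyroid).
- **If alkaline phosphatase is left out on purpose**, narrow the hepatic endpoint wording in the protocol and SAP to transaminase and bilirubin elevations, and give the reason. The type 1 diabetes term should still be added or its omission explained.

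The cost is a few table rows or one changed phrase, with no new data collection. The downside of adding alkaline phosphatase is that it can rise for non-hepatic reasons. The treatment-related endpoint limits this, but the all-causality select-AE table in SAP 7.6.5.1 does not, so that table should be read with this in mind.

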7.6.4 Adverse Events

Adverse events will be summarized by tumor type:

- Overall summary of any AEs by worst CTC grade (grade 1, 2, 3, 4, 5, unknown) presented by SOC/PT.
- Overall summary of drug-related AEs by worst CTC grade (any grade, grade 3-4, grade 5) presented by SOC/PT.

By-subject AE listing will be provided.

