7.6.5.1 Incidence of Select AE

Select AEs (see Table 7.6-1) will be summarized by tumor type for each category/subcategory for all treated subjects.

- Overall summary of any select AEs by worst CTC grade (grade 1, 2, 3, 4, 5, unknown) presented by Category or Subcategory/PT.
- Overall summary of drug-related select AEs by worst CTC grade (grade 1, 2, 3, 4, 5, unknown) presented by Category or Subcategory/PT.
- Summary of frequency of unique select AEs

The analyses will be conducted using the 100-day or for a total of 26 weeks from first on-study treatment with nivolumab whichever is earliest safety window.

By-subject select AE listing will be provided.

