7.6.6 Immune Modulating Medication

The percentage of subjects who received immune modulating concomitant medication for

- management of adverse event
- premedication
- other use
- any use
- management of drug-related select adverse event (any grade, grade 3-5) by select AE category/ subcategory
- management of IMAEs (any grade, grade 3-5) by IMAE category will be reported separately for each tumor group (percentages of treated subjects by medication class and generic term).

The following will be reported for each tumor group:

- The total medication treatment duration (excluding overlaps), duration of high dose of corticosteroid, initial dose of corticosteroid, and tapering duration (summary statistics)

The analysis will be conducted using the 100-day or for a total of 26 weeks from first on-study with nivolumab whichever is earliest safety window.

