7.6.7 Immune Mediated Adverse Events

In order to further characterize AEs of special clinical interest analysis of immune-mediated AEs (IMAE) will be conducted. Immune-mediated AEs are specific events (or groups of PTs describing specific events) that include pneumonitis, diarrhea/colitis, hepatitis, nephritis/renal dysfunction, rash, endocrine (adrenal insufficiency, hypothyroidism/thyroiditis, hyperthyroidism,

diabetes mellitus, and hypophysitis), and other specific events, considered as potential immune mediated events by investigator, that meet the definition summarized below:

- those occurring within 100 days of the last dose or for a total of 26 weeks from first on-study treatment with nivolumab whichever is earliest
- regardless of causality,
- treated with immune-modulating medication (of note, endocrine Adverse events such as adrenal insufficiency, hypothyroidism/thyroiditis, hyperthyroidism, diabetes mellitus, and hypophysitis are considered IMAEs regardless of immune-modulating medication use, since endocrine drug reactions are often managed without immune-modulating medication).

For the most recent studies, the data collection for IMAE was modified to also collect data on investigator assessment of potential IMAE including evidence of immune mediated etiology. For these studies (which will be clearly identified as such in the study specific SAP), an additional criteria accounting for immune mediated etiology or immune mediated component is also to be considered:

- with no clear alternate etiology based on investigator assessment, or with an immune mediated component

The list of MedDRA preferred terms used to identify Immune-Mediated adverse events is revisited quarterly and updated accordingly. The preferred terms used for the selection at the time of the database lock by categories will be provided.

IMAEs will be summarized for each immune mediated category / PT using the 100 days of the last dose or for a total of 26 weeks from first on-study treatment with nivolumab whichever is earliest:

- Overall summary of AEs by worst CTC grade (grade 1, 2, 3, 4, 5, unknown) presented by immune mediate Category/ PT. This summary includes all AEs that are qualified for IMAE preferred terms list, without requirement of either usage of immune modulating medications or accounting for immune mediated etiology or immune mediated component. .

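### Neurological toxicity, a named select-AE endpoint category, rests on one generic preferred term and is likely to be undercounted

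*SAP*

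**What the plan says.** SAP 4.2 sets the first secondary endpoint as "Incidence and severity of all treatment-related select AEs which are as follows" and lists eight categories, one of them neurological toxicity. Protocol 10.3.2.2 and SAP 7.6.5 give the same eight.

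SAP 7.6.5.1 makes the link to a term list: "Select AEs (see Table 7.6-1) will be summarized by tumor type for each category/subcategory for all treated subjects". Results are shown by category or subcategory and preferred term (PT). Table 7.6-1 is printed at the end of SAP Appendix 1, and its neurological row contains only "NEUROTOXICITY".

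Four other places bear on the point:
- SAP 7.6.6 reuses the categories for one line of the immune-modulating medication summary: "management of drug-related select adverse event (any grade, grade 3-5) by select AE category/ subcategory".
- SAP 7.6.7 defines immune-mediated AEs (IMAEs) as specific events "that include pneumonitis, diarrhea/colitis, hepatitis, nephritis/renal dysfunction, rash, endocrine" and some others. No neurological group is named, although the investigator may put forward other specific events. For IMAEs only, the SAP adds: "The preferred terms used for the selection at the time of the database lock by categories will be provided".
- SAP 7.6.4 gives the general table: "Overall summary of drug-related AEs by worst CTC grade (any grade, grade 3-4, grade 5) presented by SOC/PT".
- In Table 7.6-1, "SECONDARY ADRENOCORTICAL INSUFFICIENCY" is placed under the thyroid subcategory, although an adrenal subcategory exists.

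**The concern.** The term list decides which events count. A category with one generic term misses every event that has been coded more precisely. The protocol itself refers to such an event: exclusion criterion 1(i) in Protocol 6.2 mentions peripheral neuropathy as a toxicity of earlier cancer treatment. If that event occurred on study, was judged related to nivolumab and was coded under its own name, it would not enter the neurological category.

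The safety tables are the whole product of this study. It is a post-marketing commitment (Protocol 9.1), and efficacy is not analysed (Protocol 10.3.1). A neurological row at or near zero would read as reassuring when the cause was the term list. The select-AE line of the medication summary in SAP 7.6.6 would inherit the same gap.

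**Working it through.** The plan states no incidence for neurological select AEs, so there is no figure of its own to reproduce.

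**1. Count of terms in Table 7.6-1**

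| Category | PTs |
|---|---|
| Skin | 23 |
| Endocrine (adrenal 4, diabetes 2, pituitary 1, thyroid 13) | 20 |
| Hepatic | 12 |
| Renal | 9 |
| Gastrointestinal | 6 |
| Pulmonary | 5 |
| Hypersensitivity/infusion reactions | 3 |
| Neurological | 1 |
| Total | 79 |

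Neurological toxicity is the only category with a single term, and that term does little more than restate the category name.

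**2. Direction of the error.** Participants counted in the row are those with an event coded to the one listed term. They are a subset of those with any treatment-related neurological event, so the counted incidence cannot exceed the true one. Severity errs the same way. A participant with a grade 1 event under the listed term and a grade 3 event under a specific term would be shown at grade 1.

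**3. Size.** The inputs are N = 100 (70 NSCLC, 30 RCC; SAP 5) and two quantities that the documents do not give and that are assumed here:
- rate: the proportion of participants with a treatment-related neurological event, taken as 2%, 5% or 10%;
- share: the proportion of those participants with an event coded to the listed term, taken as 0%, 10% or 50%.

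Expected number counted = N × rate × share. Chance that the row shows zero = (1 − rate × share)^N.

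Example for N = 100, rate 5%, share 10%: 100 × 0.05 × 0.10 = 0.5 counted, and (1 − 0.005)^100 = 0.606.

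| N | Rate | Truly affected (expected) | Counted at share 0 / 10 / 50% | Chance of zero at share 0 / 10 / 50% | Chance of zero, complete list |
|---|---|---|---|---|---|
| 100 | 2% | 2 | 0 / 0.2 / 1.0 | 1.000 / 0.819 / 0.366 | 0.133 |
| 100 | 5% | 5 | 0 / 0.5 / 2.5 | 1.000 / 0.606 / 0.080 | 0.006 |
| 100 | 10% | 10 | 0 / 1 / 5 | 1.000 / 0.366 / 0.006 | <0.001 |
| 70 (NSCLC) | 5% | 3.5 | 0 / 0.35 / 1.75 | 1.000 / 0.704 / 0.170 | 0.028 |
| 30 (RCC) | 5% | 1.5 | 0 / 0.15 / 0.75 | 1.000 / 0.860 / 0.468 | 0.215 |

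**4. How a zero row would look.** With the Clopper-Pearson method of SAP Table 5-1, 0 of 100 has an upper 95% limit of 1 − 0.025^(1/100) = 3.62%. That limit would stand whatever other neurological terms had been reported.

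**5. The adrenal term.** It is 1 of the 20 endocrine PTs. If it occurs, a subcategory summary shows an adrenal event as thyroid; the endocrine total does not change.

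**The case against.** The strongest reply is that nothing is hidden. SAP 7.6.4 tabulates every drug-related AE by system organ class and PT with worst grade, so a specific neurological term still appears with its own incidence. Select AEs are also shown by PT and the list is printed in the SAP, so a careful reader can see that the row rests on one term. SAP 7.6.7 provides, for studies that collect the investigator's assessment, a listing of events the investigator thought immune-mediated but that missed the formal definition. In SAP 7.6.6 only one of six lines uses the select-AE categories; a treated neurological event stays under management of adverse events and under any use. The rates and shares above are assumed, and the study is descriptive with no hypothesis test.

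Much of this stands. The primary endpoint is intact, the effect on the medication summary is confined to one line, and the size cannot be derived from the documents. A select-AE table may also legitimately differ from a system organ class table, so the absence of a reconciliation step is not in itself a fault.

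None of it restores the endpoint. The number of participants with at least one neurological event, and their worst grade, cannot be rebuilt by adding PT rows, because one participant may appear in several. The category is named in both documents as part of a secondary endpoint, and the rule as written cannot estimate it.

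Two sources were not available: redacted text after the table's source line and the Data Presentation Plan cited in SAP 9. The neurological row sits directly above that source line and the multi-term rows elsewhere are legible, so a lost list of terms is unlikely but cannot be fully excluded.

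**Conclusion.** The concern holds. Table 7.6-1 limits one of the eight categories of a secondary endpoint to a single generic PT, 1 of 79 in the list. The resulting incidence and severity can only be too low. The term count and the direction of the error come from the documents. The size depends on the assumed rates and coding shares: at a 5% rate in 100 participants, between 2.5 and all 5 of the expected affected participants would be missed for shares from 50% down to 0%. This should be corrected before database lock, but it does not threaten the primary endpoint. The adrenal term under the thyroid heading is a separate, minor misplacement.

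**What to change.** Before database lock, amend Table 7.6-1 as follows:

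1. Expand the neurological category to a list of specific PTs, for example neuropathy, central nervous system inflammatory, neuromuscular and demyelinating terms, keeping the existing generic term among them. Fix the list without reference to the study's AE counts.
2. Move "SECONDARY ADRENOCORTICAL INSUFFICIENCY" to the adrenal subcategory.
3. As a minor addition, check the list against the dictionary version used to code AEs. The table cites MedDRA 16. The only coding version visible in the SAP is 20.1 or higher, stated for medical history in 7.3.4. Also provide the select-AE terms used at lock, as SAP 7.6.7 already does for IMAEs.

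The cost is an SAP table edit and an update to the programming lookup. No new data or visits are needed, and the sample size does not change.
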